6.2.3 Follow Up Period and Trial Completion

For all patients, termination of trial medication and trial completion must be recorded on the corresponding eCRF.

For patients completing the trial regularly, two safety follow-up visits will be scheduled: 10 weeks (FU1 visit) and 20 weeks (EoO visit) after the last dose of study drug (which is at Week 8, Visit 7).

Early treatment discontinuation

Patients who discontinue treatment prior to the regular EoT visit, EoT procedures should be completed as soon as possible after termination of study drug. These patients should return to the clinic for an EoO visit 20 weeks after their last administered dose of BI 655130.

Further treatment after the end of the trial

At the end of the trial, patients will be treated for their UC at the discretion of the investigator, according to local UC guidelines (e.g. ECCO guideline $\underline{R17-0243}$).

Trial completion:

Trial completion is defined as a patient having reached the EoO visit (Week 28).

Patients who complete regular treatment in study 1368-0004 will be offered to enter a long-term extension trial (1368-0017), which is currently in preparation. These patients can switch to trial 1368-0017 at EoT visit, and for these patients, their EoT visit will also be their EoO visit.

Page 58 of 82

Proprietary confidential information © 2019 Boehringer Ingelheim International GmbH or one or more of its affiliated companies

7. STATISTICAL METHODS AND DETERMINATION OF SAMPLE SIZE

7.1 STATISTICAL DESIGN - MODEL

This trial is designed as an open-label, single-arm, Phase IIa exploratory trial of BI 655130 in patients with active moderate or severe UC. For each patient, two pre-treatment blood and biopsy samples (pre-baseline at V1b and baseline at Visit 2) will serve as an internal control for the change in relevant endpoint variables. Patients should be on stable conventional treatment for their disease.

7.2 NULL AND ALTERNATIVE HYPOTHESES

It is not planned to test any statistical hypotheses in a confirmatory sense. Instead, the endpoints will be described in their entirety and evaluated by descriptive statistical methods.

For efficacy endpoints 95% confidence intervals may be presented in addition. They have to be interpreted in the perspective of the exploratory character of the study, i.e. confidence intervals are considered as interval estimates for effects.

7.3 PLANNED ANALYSES

Due to the exploratory nature of this trial, all statistical descriptions of clinical results will be descriptive and no formal testing for significance of differentiation will be provided.

Gene expression of mucosal biopsies as assessed by RNAseq will be analysed to identify the total number of deregulated genes over time. Deregulated genes are those genes that react to the drug administration over time (compared to baseline) in a significant manner. Quantitative criteria for the selection of deregulated genes are given below in Section 7.3.1 after the required details of the gene expression analyses including pre-processing of raw read count values are described.

The gene expression analysis includes initially all genes and all determined read counts. This means, if no gene expression values have to be excluded due to technical or other reasons, there is one read count value per person, per gene and per time point (pre-baseline, baseline, and during treatment period at time points indicated in the Flow Chart).

Based on these raw read count values (refer to Section 5.5.1) the DESeq2 method, one of the standard methods to analyse RNAseq data, is used for the gene expression analysis and for the identification of deregulated genes. In the following key properties and special characteristics of this method with regard to the considered analysis will be delineated. For a detailed description of this method and further statistical details please refer to Love et al. (R16-5384).

Boehringer Ingelheim		03 Apr 2019
BI Trial No.: 1368-0004		
c10710598-04	Trial Protocol	Page 59 of 82

Starting with the raw read counts the DESeq2 method models these counts following a negative binomial distribution with a certain mean and dispersion parameter. In more detail, the read count K_{ij} for gene i in sample j is described by

 $K_{ij}{\sim}NB(mean=\mu_{ij}, dispersion=\alpha_i).$

The mean consists of a design specific quantity q_{ij} scaled by a normalization factor s_{ij} . The basic idea of the DESeq2 method is now to fit a generalized linear model of the negative binomial family with a logarithmic link. Thereby the quantity q_{ij} of each gene is described by $\log_2 q_{ij} = \sum_r x_{jr} \beta_{ir}$ with design matrix elements x_{jr} and coefficients β_{ir}

To get interpretable results several pre-processing steps are needed to correct e.g. for different sequencing depth. For most of these steps the default approach (option) in the DESeq2 software package is used. In detail for the actual study design the following steps are conducted:

- Genes for which the sum of all counts is less than or equal to 1 are excluded.
- Genes with a high pre-treatment variability are excluded from the analysis: A gene is excluded if it meets the regular criteria (>1.5 fold deregulation, FDR adjusted p value <0.01) of being differentially expressed between the two consecutive pre-treatment time points. Hereby, the adjusted P-value is based on the Wald test including only the two pre-treatment time points (i.e. pre-baseline and baseline).
- Read Counts are normalized using the median-of-ratios method of Anders and Huber (R17-0129):

The normalization constants s_{ij} are considered constant within a sample, i.e. $s_{ij} = s_j$. The value s_j is calculated by

 $s_j = \text{median}_{i:K_i^R \neq 0} \frac{K_{ij}}{K_i^R} \text{ with } K_i^R = \left(\prod_{j=1}^m K_{ij}\right)^{1/m}.$

- Estimation of the dispersion parameter α_i : For each gene, an estimate of the dispersion is found which maximizes the Cox Reidadjusted profile likelihood (R17-0128).
- Handling of outlier using Cook's distance (using the default option cooksCutoff = 0.99 in the DESeq2 package): Cook's distance (R17-0126) quantifies how much a single sample is influencing the fitted coefficients for a gene, and a large value of Cook's distance is intended to indicate an outlier count. No changes to the default setting are conducted.

After these pre-processing steps the actual expression analysis can be conducted (see Section 7.3.1)

Adherence to the protocol (such as inclusion/exclusion criteria, times of measurement, compliance with intake of trial medication, treatment dispensing errors, prohibited concomitant medication, completeness and consistency of data) will be checked. Important protocol violations (IPVs) will be identified in the Trial Statistical Analysis Plan (TSAP).

Boehringer Ingelheim		03 Apr 2019
BI Trial No.: 1368-0004		_
c10710598-04	Trial Protocol	Page 60 of 82

The patient set for the primary evaluation of gene expression will include all patients who completed trial medication and trial through EoT visit and who provide at least one evaluable baseline and one evaluable post-baseline biopsy RNA measurement. The patient set for the safety analyses will include all patients who received at least one dose during the trial. Details on the analysis sets and further analysis sets e.g. for the BM assessments, will be defined in the TSAP.

7.3.1 Primary endpoint analyses

For all genes, which are not excluded in the pre-processing step the Wald test (included as the default test for significance testing in the DESeq2 package) is conducted to identify whether this gene is deregulated or not for a certain time point.

Only one baseline value is included in the model, namely the last value before first drug administration, but all post-treatment values. The generalized linear model includes time as additional covariable (and also subject as covariable). So every time point is an additional design matrix element x_{jr} and the model fit leads (for every gene i) to β_{ir} estimates for each time point. To test changes from baseline the contrasts of these β coefficients (or more precisely the difference between post-treatment estimate and baseline) are divided by their estimated standard error, resulting in a z-statistic, which is compared to a standard normal distribution. Hereby the default option *lfcThreshold* = 0 is utilized, meaning a null hypothesis of no difference.

The Wald test results in a P-value and an FDR adjusted P-value for each gene and each posttreatment time point. A gene has a small P-value at a certain time point if there is a significant difference to the pre-treatment estimate, meaning an adjusted mean value clearly lower or higher compared to baseline. The calculation of the FDR adjusted P-value is (by default in the DESeq2 package) based on the Benjamini and Hochberg (P05-11198) approach (*pAdjustMethod* = "*BH*") combined with independent filtering (*independentFiltering* = *TRUE*). The independent filtering is based on the mean of normalized counts as a filtering statistic (R17-0127). A threshold on the filter statistic is found which optimizes the number of FDR adjusted P-values lower than a significance level of *alpha*=0.1 (default setting). In doing so, genes with very low counts at all time points are excluded and no FDR adjusted P-value is reported for these genes.

Beside the FDR adjusted P-value the Wald test calculates for every gene and every time point the difference in fold change compared to the baseline estimate. To get a conservative and stringent approach for the identification of deregulated genes both of these measurements, the FDR adjusted P-value based on the Wald test and the-fold change, are used to identify deregulated genes.

Definition of deregulated genes

A gene is defined as deregulated at time point i if the FDR adjusted P-value of the Wald test is below 0.01 and if |fold change (time point i vs. baseline)| \geq 1.3.

The total number of deregulated genes per time point will be reported.

Boehringer Ingelheim		03 Apr 2019
BI Trial No.: 1368-0004		
c10710598-04	Trial Protocol	Page 61 of 82

Sensitivity analyses for example evaluation of alternative thresholds for the classification of genes (deregulated vs. not deregulated) will be provided in the TSAP. In particular if e.g. the number of identified deregulated genes is very large a smaller threshold for the FDR adjusted P-value might be considered.

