7.3 TREATMENT COMPLIANCE

Treatment compliance will be summarised overall via total volume infused (as a % of planned) for the FAS using descriptive statistics (N, mean, SD, minimum, median, maximum). For the patients who discontinued the study treatment prematurely only the visits on or before premature discontinuation will be used for the calculation of overall compliance.

The by visit compliance will be listed only.

The number and percentage of patients with the following overall compliance categories will be presented:

• "< 80% of planned",

- "80 to 120% of planned" and
- "> 120% of planned".

7.4 **PRIMARY ENDPOINTS**

The pre-processing of the raw read count values will be conducted as described in Section 7.3 of the CTP. The primary endpoint will be evaluated for the CAS. The analysis will be performed as defined in Section 7.3.1 of the CTP. The FDR adjusted P-value based on the Wald test and the log2 fold change, are used to identify deregulated genes.

Definition of deregulated genes

A gene is defined as deregulated at time point i if the FDR adjusted P-value of the Wald test is below 0.01 and if |fold change (time point i vs. baseline)| \geq 1.3.

The total number of deregulated genes per (post-baseline) time point (V2, V3, V4, V7 and EoT) will be reported.

The following sensitivity analyses may be conducted:

- The number of deregulated genes will be evaluated for the FAS in case this analysis set differs (with regard to RNA analyses) from the CAS
- In case the number of identified deregulated genes is very large (> 5000 deregulated genes at all time points) a smaller threshold for the FDR adjusted P-value will be considered
- In case the number of identified deregulated genes is empty (or includes less than 50 genes at all time points) the 50 genes with the smallest FDR adjusted P-values will be listed per (post-baseline) time point

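### The low-count filter behind the primary gene count is tuned at an adjusted P of 0.1 although genes are counted at 0.01; matching the two is a free improvement of low materiality

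*Protocol*

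**What the plan says.** Protocol 7.3.1 tests each gene at each post-treatment time point with a Wald test in DESeq2 and adjusts the P-values by Benjamini-Hochberg with independent filtering switched on. On the filter it says: "The independent filtering is based on the mean of normalized counts as a filtering statistic". The threshold on that statistic is the one that "optimizes the number of FDR adjusted P-values lower than a significance level of *alpha*=0.1 (default setting". The consequence for filtered genes is that "genes with very low counts at all time points are excluded and no FDR adjusted P-value is reported for these genes", so a filtered gene cannot enter the primary count.

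The counting rule comes at the end of the same section: "A gene is defined as deregulated at time point i if the FDR adjusted P-value of the Wald test is below 0.01", with an absolute fold change of at least 1.3 also required. SAP 7.4 (Primary Endpoints) repeats both criteria. For the method it points back to the protocol: "The analysis will be performed as defined in Section 7.3.1 of the CTP". It gives no filter alpha of its own.

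SAP 7.4 also allows a smaller FDR threshold as a sensitivity analysis if more than 5000 genes are deregulated at all time points. It does not say whether the filter alpha would change with it.

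**The concern.** In much RNA sequencing work the filter is a background setting. Here the number of rejections is itself the primary endpoint, so a step that chooses its threshold by maximising rejections shapes the endpoint directly. One would expect it to maximise rejections at the level that defines the endpoint. The plan uses a level ten times looser (0.1 / 0.01 = 10).

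The expected direction is clear. A low-count gene has a large standard error and can rarely reach a strict cut, but it still adds to the multiple-testing burden. A filter tuned to the looser cut tends to keep more such genes than suits the stricter one. What is at stake is a few genes of yield in a trial of 10 patients, and a primary count that depends on a package default for which no reason is given.

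**Working it through.** **1. Is there a figure to reproduce?** No. Neither document states an expected gene count or power. Protocol 7.7 says that the sample size of 10 does not rest on a power calculation. The check is therefore one of the text, an inequality and a simulation.

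**2. The text.** Filter tuning level: 0.1 (Protocol 7.3.1). Counting level: 0.01 (Protocol 7.3.1 and SAP 7.4). No sentence links the two.

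**3. The inequality.** Let R_a(t) be the number of genes with adjusted P below a when genes under mean-count threshold t are dropped. The plan picks t* to maximise R_0.1(t) and then counts at 0.01. If t* is the plain maximiser on a fixed grid, R_0.01(t*) ≤ max over t of R_0.01(t). Before the fold-change cut, the plan's setting can therefore equal but never exceed the yield of a filter tuned at 0.01. The 1.3-fold cut comes afterwards, and a smoothed selection rule breaks the strict inequality, so the size needs simulation.

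**4. Simulation inputs.** From the documents: n = 10, adjusted P < 0.01, absolute fold change ≥ 1.3, Benjamini-Hochberg, mean-count filter, and a null of no difference ("Hereby the default option *lfcThreshold* = 0 is utilized, meaning a null hypothesis of no difference"). Assumed, not in the documents: 25,000 genes; ln mean count normal with mean 3 and SD 3; 2%, 10% or 30% of genes changed; SD of ln fold change 0.5 or 1.0; dispersion 0.1 or 0.3; 50 candidate thresholds; 8 runs per setting.

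Standard error of the ln fold change: SE = sqrt(2 × (1/mu + dispersion) / n). With dispersion 0.1:
- mu = 1: sqrt(2 × 1.1 / 10) = 0.469
- mu = 100: sqrt(2 × 0.11 / 10) = 0.148

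The SE of the low-count gene is about three times as large, which is why a stricter cut favours a higher filter threshold.

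**5. Results.** Mean number of genes meeting both criteria, filter tuned at 0.1 → at 0.01. The percentage is the mean of the run-by-run changes.

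| Changed | SD ln FC | Dispersion | Plain maximum | Smoothed curve |
|---|---|---|---|---|
| 2% | 0.5 | 0.1 | 73 → 74 (+1.9%) | 72 → 74 (+1.7%) |
| 2% | 0.5 | 0.3 | 15 → 15 (+5.8%) | 14 → 15 (+6.8%) |
| 2% | 1.0 | 0.1 | 198 → 200 (+0.6%) | 200 → 201 (+0.1%) |
| 2% | 1.0 | 0.3 | 121 → 123 (+1.4%) | 123 → 123 (+0.3%) |
| 10% | 0.5 | 0.1 | 477 → 481 (+0.7%) | 448 → 453 (+1.3%) |
| 10% | 0.5 | 0.3 | 124 → 127 (+2.5%) | 118 → 120 (+1.6%) |
| 10% | 1.0 | 0.1 | 1109 → 1112 (+0.2%) | 1121 → 1122 (+0.1%) |
| 10% | 1.0 | 0.3 | 714 → 717 (+0.4%) | 727 → 729 (+0.3%) |
| 30% | 0.5 | 0.1 | 1634 → 1644 (+0.7%) | 1612 → 1631 (+1.2%) |
| 30% | 0.5 | 0.3 | 501 → 505 (+0.7%) | 505 → 512 (+1.5%) |
| 30% | 1.0 | 0.1 | 3591 → 3598 (+0.2%) | 3603 → 3605 (+0.1%) |
| 30% | 1.0 | 0.3 | 2465 → 2475 (+0.4%) | 2426 → 2430 (+0.2%) |

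In the setting with about 15 genes, the gain of 6% to 7% is 0.8 to 1.0 gene. A separate simulation, also with both criteria and the plain maximum, gave mean gains of about 0% to 3%, and 2 genes where about 18 were found (2/18 = 11%).

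Single results scatter more. Under the plain maximum no run lost genes, and the largest relative gain was 27.3% in the setting with about 15 genes (at most 3 genes). Under the smoothed rule the lowest run was −1.7%. In a further five-visit check, one visit with 66 genes gained 9%, about 6 genes.

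**6. Why yield moves.** The 0.01-tuned filter usually removed somewhat more genes, for example 18% against 12% in the 30% / 0.5 / 0.1 setting under the plain maximum.

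**7. Error control.** The false discovery proportion was taken on adjusted P < 0.01, before the fold-change cut. In settings with about 100 genes or more it was 0.6% to 1.4% under either tuning. In sparser settings it ran from 0.3% to 2.2% and was higher under the 0.01 tuning, but 8 runs of about 15 genes are only about 120 genes. There, 0.63% against 1.67% is a difference of about one gene (0.0104 × 120 = 1.2), too few to read anything into.

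**The case against.** The strongest reply is that this is a prespecified package default, openly labelled as such, in an exploratory trial with no confirmatory test (Protocol 7.2) and no power target. The effect is small, and its direction, a slightly lower count, suits the conservative approach that Protocol 7.3.1 says it wants. For a sparse result, SAP 7.4 already offers a list of the 50 genes with the smallest adjusted P-values per time point.

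Most of this stands as an argument about weight. It does not explain the setting. The plan chose its own cut of 0.01 for stringency, and a filter tuned to a different level adds no principled stringency; it only spends multiplicity on genes unlikely to pass. The list of 50 is optional, applies only if fewer than 50 genes are found at all time points, and does not change the count.

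A reader might also infer that the threshold is searched separately at each visit, so that the visits' counts rest on different gene sets and need one common threshold. Protocol 7.3.1 does not say so: it speaks of a single threshold being found and of genes with low counts at all time points. A common threshold would also need a selection rule and can give back the gain at visits with few genes. Nor do the documents support a change to the comparison of the two pre-treatment samples: Protocol 7.3 states no filter alpha for it, and more rejections there would remove genes from the primary analysis.

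**Conclusion.** The mismatch is certain from the text and bears on the rule that produces the primary endpoint. Its consequence is small: an expected loss of about 0% to 3% of the count, or one or two genes where very few are found. These sizes rest on assumed distributions of mean counts, dispersion and effects, on a normal approximation to the Wald statistic, and on few runs per setting. The average direction agrees across the simulations; a single data set could move slightly the other way under a smoothed rule.

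It would be tempting to conclude that the primary count is invalid or its error rate inflated. The documents do not support that: the filter statistic is the mean normalised count, and the 0.01 cut is applied whichever tuning is used. The point is a free improvement of low materiality. The mismatch would widen if SAP 7.4's smaller FDR threshold were used with the filter left at 0.1.

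**What to change.** In Protocol 7.3.1 and SAP 7.4, state that the independent-filtering alpha equals the counting cut of 0.01. Add that, if a sensitivity analysis under SAP 7.4 uses another FDR threshold, the filter is re-run with alpha equal to that threshold. If the sponsor prefers to keep 0.1, one sentence should say why.

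The cost is one argument in the program and one SAP sentence, with no new data and no change to the test, the adjustment method or the definition of a deregulated gene. Because the setting alters the primary count, it should be fixed before the counts are known.

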7.3.2 Secondary endpoint analyses

The efficacy endpoints, such as percent change in CRP, will be evaluated descriptively, along with exact 95% confidence intervals, if feasible. Additionally the original as well as change from baseline values for all time points from baseline up to Week 12 will be presented. If the data appears to be very skewed then a log transformation and a summary statistic on the log scale will also be presented. Summary plots will also be produced if necessary.

The binary efficacy endpoint patient with clinical remission based on Mayo score at Week 12 will be described using patient frequencies and percentages. Exact 95% confidence intervals will additionally be provided for the proportion of patients, if feasible. Furthermore shift tables from baseline up to Week 12 will be produced for the Mayo score.

Analysis of safety and tolerability is described in Section 7.3.4.

Page 62 of 82

Proprietary confidential information © 2019 Boehringer Ingelheim International GmbH or one or more of its affiliated companies

7.3.4 Safety analyses

Safety will be assessed for the endpoints listed in Section 5.3. All treated patients (that is all patients who received at least one dose of the study drug) will be included in the safety analysis. In general, safety analyses will be descriptive in nature and will be based on BI standards. No hypothesis testing is planned.

Statistical analysis and reporting of AEs will concentrate on treatment-emergent AEs. To this end, all AEs occurring between start of treatment and end of the residual effect period will be considered 'treatment-emergent'. The residual effect period is defined as 140 days after the last dose of trial medication. AEs that start before first drug intake and deteriorate under treatment will also be considered as 'treatment-emergent'. Drug related AEs, as a secondary endpoint of this trial, will be tabulated by system organ class and preferred term (PT) after coding according to the current version of the Medical Dictionary for Drug Regulatory Activities (MedDRA).

In addition, the frequency, severity, and causal relationship of AEs will be tabulated by system organ class and PT after coding according to the current version of the MedDRA.

Laboratory data will be analysed both quantitatively as well as qualitatively. The latter will be done via comparison of laboratory data to their reference ranges. Values outside the reference range as well as values defined as clinically relevant will be highlighted in the listings.

Vital signs, physical examinations, or other safety-relevant data observed at screening, baseline, during the course of the trial and at the end-of-trial evaluation will be assessed with regard to possible changes compared to findings before start of treatment.

For vital signs, the differences from baseline will be evaluated. Relevant ECG findings will be reported as AEs.

Page 63 of 82

Proprietary confidential information © 2019 Boehringer Ingelheim International GmbH or one or more of its affiliated companies

